- out-of-hospital consultations (general practitioner, physical therapist, psychologist, other);
- institutionalized care (*e.g.*, nursing home, rehabilitation center);

- formal home care (e.g., housekeeping, personal care, nursing);
- use of medication.

Out-of-pocket expenses included the following used resources:

- over-the-counter medication;
- informal help at home;
- non-reimbursable devices;
- health-related travel;
- additional expenses by informal primary caregivers.

Productivity loss focused on the impact of CLI and DBS on lost working hours from paid work only and was addressed exploratory. Lost working hours in the subgroup of patients with a paid job were quantified by summing the:

- number of days of sick leave multiplied with patient's mean number of working hours a day;
- number of affected days at work multiplied with the factor "(10 minus self-reported efficiency)/10" with self-reported efficiency reported on a scale from 0 (did not accomplish anything at all) to 10 (worked as efficiently as always).

Lost working hours in the subgroup of primary caregivers with a paid job were estimated as supplied by those caregivers.

Data on use of health care resources were derived from hospital records, electronic clinical report forms and the Medical Consumption Questionnaire (iMCQ) completed by patients or their primary caregiver at quarterly intervals.²² The questions on the out-of-pocket expenses presumed relevant were added to the iMCQ. To quantify health-related travel, the numbers of contacts with distinct health care providers were counted and combined with standardized distances in kilometers between patients' homes and local health care providers,²³ except for the geographically more thinly scattered DBS treatment centers in which case the mean of the actual distances in kilometers between postal codes of providers and patients were used.²⁴ The result per patient was multiplied by two considering the 'to and from' of traveling. Data on sick leave from work and lowered efficiency while at work from patients as well as lost working hours by the primary informal caregiver were gathered with an adjusted version of the Productivity Costs Questionnaire (iPCQ).²⁵

Unit costs and costing

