If opportune, unit costs of (non-)hospital resources, working hours lost, and time spent on the patient by the primary care-giver were obtained from the most recent Dutch Manual on Costing in health care research (DMC).²³ The unit costs of the (re)placement of the neurostimulator system and of the tube and pump system (re)placements were based on unit costing sheets for distinct hospital care resources from the treatment center with the highest number of inclusions and subsequently capitalized based on a 5-year depreciation period (reflecting the lengths of their life cycles) in order to allow for a robust estimate of the difference in yearly treatment costs by study arm, irrespective of the chosen study's time horizon. The same hospital unit costing sheets, existing rates for mutual services excluding VAT, or passer-by prices (e.g., AMC Passantenprijslijst OZP, 2020) were used for observed diagnostic examinations and therapeutic procedures not listed in the DMC. Unit costs for medication were gathered from the Dutch Pharmaceutical Compass assuming standard prescriptions.^{26,27} The unit cost of lost working hours at the mean age of the included working patient at baseline was used, non-specific for gender. In case of prolonged continuous sick leave longer than the friction period, the friction cost method was applied.²⁸ The length of the friction period in days was calculated as the average over the study's observation period 2015-2020, weighted for the

yearly number of included patients, and equaled 97 days.^{23,29} Table EE1-S in the Supplementary Material shows unit cost of the resources used. Unit costs held for the base year 2020; unit costs originating from different calendar years were price-indexed with general yearly consumer price indices from Statistics Netherlands.³⁰

Costs of resources used were calculated by multiplying the frequency of distinct resources used with their respective (depreciated) unit costs. Volumes and costs (of health care used, out-of-pocket expenses, and productivity loss) are reported separately as (subtotal and total) means per patient per study arm.

Analyses were adjusted if deemed necessary in case of Parkinson-related or Parkinson non-related outliers in costs or QALYs. If related to Parkinson's disease, these were included and reported, if caused by unrelated comorbidities, these could have been excluded.

Health outcomes

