Other hospital care			
Emergency department visit			
Hospital stay (in days)			
neurology ward			
psychiatric ward			
intensive care unit			
other			
Outpatient consultation			
neurologist			
CLI/DBS-nurse			
neurosurgeon			
gastroenterologist			
PEG-nurse			
psychiatrist			
(neuro)psychologist			
Imaging diagnostics			
MRI brain			
CT brain			
X-ray DBS leads			
CT abdomen			
ultrasonography abdomen			
Therapeutics			
ex-plantation (battery, lead,...)			
related medication			

BCa CI: bias corrected and accelerated confidence interval, CLI: continuous levodopa infusion, CT: computed tomography, DBS: deep brain stimulation, EKG: electrocardiogram, MRI: magnetic resonance imaging, NA: not applicable, PEG: percutaneous endoscopic gastrostomy

*P-values not reported for use of resources

**Differences rounded to zero keep their sign

Table EE2b. Mean per patient use of non-hospital resources and productivity loss by strategy*

	CLI (n=)	DBS (n=)	Difference** CLI vs DBS
	Mean (95% BCa CI)	Mean (95% BCa CI)	Mean (95% BCa CI)
Non-hospital care			
Medication			
CLI-cassettes related medication			
Out-of-hospital consultation			
general practitioner			
occupational therapist			
physiotherapist			
speech therapist			
dietician			
social worker			
psychologist			
rehabilitation physician			
company physician			
Other institutional stay			
nursing home day			
rehabilitation center day			
Formal home care			
house holding			
personal			
home nursing			
Equipment			
walking devices			
other living aids			
Productivity loss in hours			
absenteeism			
presenteeism			

BCa CI: bias corrected and accelerated confidence interval, CLI: continuous levodopa infusion, DBS: deep brain stimulation

* P-values not reported for use of resources

** Differences rounded to zero keep their sign

Table EE3. Mean per patient costs by strategy

	CLI (n=)	DBS (n=)	Difference* CLI vs DBS	P-value
	Mean costs (95% CI)	Mean costs (95% CI)	Mean costs (95% CI)	
Hospital care				
Screening for suitability				
Continuous Levodopa Infusion				
Deep Brain Stimulation				
Emergency department visit				
Hospital in patient stay				
Outpatient consultation				
Diagnostics				
Therapeutics				
Non-hospital care				
Medication				
Out-of-hospital consultation				
Other institutional stay				
Formal home care				
Equipment				
Out-of-pocket expenses				
Productivity loss				
Total health care costs				
Total societal costs				

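### The presenteeism formula gives days, but is summed, tabulated and priced as hours; coded literally, that row is too low by a factor equal to the hours in a working day

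*SAP*

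**What the plan says.** The HEAP (Cost components, Sources) restricts productivity loss to paid work and calls it exploratory. It then gives the calculation for patients: "Lost working hours in the subgroup of patients with a paid job were quantified by summing the" two products.

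- Absenteeism: "number of days of sick leave multiplied with patient's mean number of working hours a day".
- Presenteeism: "number of affected days at work multiplied with the factor" "10 minus self-reported efficiency)/10", where efficiency is self-reported "on a scale from 0 (did not accomplish anything at all) to 10 (worked as efficiently as always".

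The unit used downstream is the hour. Tables EE2b and EE3b-S list absenteeism and presenteeism together under "Productivity loss in hours". Table EE1-S gives the unit of both as the hour. Under Unit costs and costing the HEAP states: "The unit cost of lost working hours at the mean age of the included working patient at baseline was used". The same section obtains costs as volume times unit cost. Table EE3 then carries a productivity-loss row above the total societal costs, with a column for P-values.

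The protocol (section 12.5) makes the societal perspective the basis of the economic evaluation. It includes impaired presence at work without calling it exploratory.

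**The concern.** The two products do not have the same unit. The first contains "mean number of working hours a day" and is in hours. The second multiplies days by a number between 0 and 1 that has no unit, so it is in day-equivalents. Their sum is called hours and is multiplied by an hourly price. Nothing elsewhere in the HEAP or protocol converts affected days into hours.

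The consequence is easy to see for one patient. Someone who works one day at half efficiency is credited with 0.5, which is then priced as half an hour instead of half a working day.

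At stake are one published cost row and the societal total that contains it. The HEAP was finalised and uploaded before database lock so that it could serve as the specification. An analyst who codes from it, or a reader who tries to reproduce the result, would obtain the wrong volume.

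**Working it through.** The plan states no productivity-loss volume or cost, so there is no figure to reproduce. The check is one of units, followed by a scale calculation on assumed inputs.

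**Notation.** A = sick-leave days; D = affected days at work; h = mean working hours a day; f = (10 − efficiency)/10.

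**Units**

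- As written: A × h [hours] + D × f [days].
- Unit-consistent: A × h + D × h × f [hours].
- Ratio on the presenteeism row: (D × h × f)/(D × f) = h.
- Ratio on total patient productivity loss: (A × h + D × h × f)/(A × h + D × f).

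**Inputs.** Only the formulas and the expected cost difference of EUR 34,174 a year (protocol 4.4) come from the documents. The documents give no value for A, D, h, efficiency, hourly price or share of patients in paid work. All of these are assumptions below.

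**Presenteeism row.** With D = 40 and efficiency 7, f = 0.3.

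- As written: 40 × 0.3 = 12.
- With h = 4: 40 × 4 × 0.3 = 48 hours, 4 times as much.
- With h = 8: 40 × 8 × 0.3 = 96 hours, 8 times as much.
- A shorter day gives a smaller factor: with h = 2 it is 2.

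**Total patient productivity loss, D = 40**

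| h | Efficiency | A | As written | Unit-consistent | Ratio |
|---|---|---|---|---|---|
| 4 | 7 | 20 | 92 | 128 | 1.39 |
| 4 | 7 | 60 | 252 | 288 | 1.14 |
| 8 | 7 | 20 | 172 | 256 | 1.49 |
| 8 | 7 | 60 | 492 | 576 | 1.17 |
| 8 | 5 | 20 | 180 | 320 | 1.78 |
| 8 | 5 | 60 | 500 | 640 | 1.28 |

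The total reaches a ratio of h only when A = 0.

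**Mean societal cost per patient.** The shortfall is D × f × (h − 1) × hourly price × share in paid work. With D = 40, f = 0.3 and EUR 35 an hour:

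- h = 4: 12 × 3 × 35 = EUR 1,260 per working patient. At 10% to 30% in paid work this is EUR 126 to 378 per patient.
- h = 8: 12 × 7 × 35 = EUR 2,940 per working patient, or EUR 294 to 882 per patient.
- Against EUR 34,174: 126/34,174 = 0.4% and 882/34,174 = 2.6%.

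Varying D from 20 to 100 days, with the other assumptions kept, widens the range to EUR 63 to 2,205 (0.2% to 6.5%).

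**Difference between arms.** These amounts are shifts in the level of an arm. If h, price and share in paid work are equal in the two arms, the CLI minus DBS difference moves by (h − 1) × price × share × (difference in mean D × f between arms). It does not move if presenteeism is equal. If one arm loses 12 day-equivalents and the other 6, it moves by half the amounts above, EUR 63 to 441. The direction depends on which arm has more presenteeism.

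**The case against.** The best defence is that this is a dropped phrase and not a wrong calculation. The lead-in speaks of lost working hours, the tables are headed in hours and the price is per hour, so hours were evidently the intent. The syntax is not in the documents and may already multiply by hours a day. That stands: the documents show a faulty specification, not a result that has gone wrong. It is also a reason to correct the text, because the neighbouring bullet states the multiplier explicitly and this one does not.

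The reach is limited too. Productivity loss is labelled exploratory, covers paid work only and does not enter the health care perspective, the PDQ-39 change or the QALYs. Caregivers' lost hours are taken as the caregivers supply them and do not pass through this formula. All of this stands, and it lowers the weight of the point. It does not remove it, because Table EE3 lists productivity loss above total societal costs.

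A reader might infer that lost productivity, or even societal cost, is understated 4- to 8-fold. The documents do not support that. The factor belongs to the patient presenteeism row alone, and 4 to 8 is only an assumed length of working day.

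**Conclusion.** The formula is wrong as written: it adds days to hours and prices the sum per hour, and no other section repairs it. That part is certain and rests on the text alone.

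The size is conditional on literal coding. The patient presenteeism row would then be too low by exactly the mean working hours a day. Total patient productivity loss would be too low by about 1.1 to 1.8 times when there are 20 or 60 sick-leave days. Mean societal cost per patient would be too low by about EUR 126 to 882, given 40 affected days, efficiency 7/10, EUR 35 an hour, 4 to 8 hours a day and 10% to 30% in paid work.

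*Understated* describes the cost level in each arm. It should not be read as a statement about the cost difference, where the effect could have either sign and is probably small. Nothing in the documents suggests that the cost-effectiveness conclusion turns on this row. It is a small correction that should be made because a published cost line and a societal total depend on it.

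**What to change.** Rewrite the second bullet in the HEAP (Cost components, Sources) so that the presenteeism term is: affected days at work × the patient's mean working hours a day × (10 − efficiency)/10. If the adjusted iPCQ records affected time in some other way, state instead how it becomes hours.

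Then confirm that the analysis syntax applies the conversion before the presenteeism rows of Tables EE2b and EE3b-S and the total societal costs of Table EE3 are produced. If the syntax already does so, only the text changes.

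The cost is one phrase and one check of the code. No new data are needed, since the absenteeism term already requires hours a day for each working patient.

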12.5 Cost Effectiveness analysis (CEA)

The economic evaluation of CLI against DBS treatment will be performed based on intention-to-treat as a cost-effectiveness and cost-utility analysis from a societal perspective with the costs per unit on the PDQ-39 and the costs per quality adjusted life-year (QALY) as the primary outcomes respectively. The primary outcome of the cost-effectiveness analysis is closely related to the primary clinical outcome, the PDQ-39. The cost-utility analysis is considered mandatory to enable health policy makers allocating scarce health care resources across disease populations, across interventions, and across health sectors, based on explicit efficiency criteria. It is expected that CLI generates higher costs than DBS during the year of follow-up and should therefore sufficiently pay off compared with DBS in terms of increased effectiveness in order to be affordable for patient populations that might benefit from both treatments. It is yet unclear whether CLI actually pays off sufficiently.

Incremental cost-effectiveness and cost-utility analyses will be performed for a willingness-to-pay value of €120,000 (for rationale, see sample size calculation) based on the net health benefit transformations of the respective incremental cost-effectiveness ratios and assuming reasonably normally distributed cost data. The time horizon in the study equals 1 year. With this time frame no discount rate will be applied for effects and costs to account for time preference. However, given the 5-year life-cycle of the studied devices (neurostimulator, tube, and pump) and the marked contrast of costs in the first year of treatment compared to subsequent years within the life-cycle period, we will depreciate the initial add-on intervention costs (placement of neurostimulator for DBS and tube and pump placement for CLI) over five years.

One-way and multi-way probabilistic sensitivity analyses will be performed for the length of the friction period (3-6 months), and choice of UK rather than Dutch tariffs of time trade-off ratings of health states.

Additional analyses will be performed with the assessments 24 and 36 months after start of treatment, to assess the longer term costs and benefits of both treatments more precisely.

Cost analysis

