The primary objective of the economic evaluation is to estimate the cost-effectiveness and cost-utility of CLI treatment versus DBS treatment in the first year of follow-up after treatment initiation. The results of the cost-effectiveness analysis (CEA) allow for local decision making on the economically most optimal treatment approach for patients with PD, based on the clinically relevant health outcomes regarding quality of life in particular, while the cost-utility analysis (CUA) provides information for health policy decision makers to decide upon efficient and affordable health care in general, based on nationally accepted evaluation criteria regarding costs per QALY in view of patients' disease burden.

Types of economic evaluation

The economic evaluation of CLI against DBS was conducted alongside the INVEST clinical trial with individual patient-level data. The costs per unit change on the PDQ-39 summary index score at 12 months follow-up versus baseline and the costs per quality adjusted life year (QALY) were the primary economic outcomes. Incremental cost-effectiveness (ICER) and cost-utility (ICUR) ratios were calculated as the costs difference divided by the difference in effect for CLI minus DBS treatment.

Jurisdiction

The trial was conducted in the Netherlands, where health insurance is obligated for inhabitants and health care is offered by public and private providers.

Perspective, time horizon and discounting

Both health care and societal perspectives were taken into account with a time horizon of 12 months following index surgery. Because the time horizon was 12 months, no discounting was performed.

Cost components

Costs encompassed health care costs, out-of-pocket expenses by patients and family members and costs of productivity loss due to sick leave from work (absenteeism) or lowered efficiency while at work (presenteeism).

Sources

Health care costs covered the use of the following use of resources:

- screening for appropriateness of treatment indication;
- index treatments CLI with infusion devices or DBS with stimulation devices;
- emergency departments visits;
- inpatient hospital admissions at neurology, psychiatry, the intensive care, or other units;
- outpatient hospital consultations (*e.g.*, medical specialist, specialist nurse);
- diagnostic procedures (*e.g.*, imaging by MRI, CT, ultrasonography or X-ray);
- therapeutic procedures (*e.g.*, ex-plantation, revision tube or other material, medication);

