Appendix IV — Supplementary health economics tables

Table EE1-S. Dutch unit costs (€) for resources used

Resource	Unit	Unit costs in 2020 euros	Source
Screening for suitability			
preop. outpatient consultation	visit		DMC
inpatient stay	day		DMC
on/off-phase evaluation	procedure		hospital ledger
evaluation / nasogastric tube	procedure		passer-by rate
vitamin examinations	procedure		passer-by rate
other laboratory	procedure		passer-by rate
preop. anesthetic evaluation	procedure		hospital ledger
EKG	procedure		passer-by rate
MRI-brain	procedure		DMC
Infusion			
CLI-pump	device*		hospital ledger
CLI-cassettes	cassette		hospital ledger
PEG-jejunostomy placement	procedure*		passer-by rate
tube replacement	procedure*		passer-by rate
Stimulation			
(re)implantation	procedure*		passer-by rate
electrode replacement	procedure		hospital ledger
extension cable replacement	procedure		passer-by rate
battery exchanges	exchange		hospital ledger
Other hospital care			
Emergency department visit	visit		DMC
Hospital stay (in days)			
neurology ward	day		DMC
psychiatric ward	day		DMC
intensive care unit	day		DMC
other	day		DMC
Outpatient consultation			
neurologist	visit		DMC
CLI/DBS-nurse	visit		hospital ledger
neurosurgeon	visit		DMC
gastroenterologist	visit		DMC
PEG-nurse	visit		hospital ledger
psychiatrist	visit		DMC
(neuro)psychologist	visit		DMC
Imaging diagnostics			
MRI brain	procedure		DMC
CT brain	procedure		DMC
X-ray DBS leads	procedure		hospital ledger
CT abdomen	procedure		passer-by rate
ultrasonography abdomen	procedure		passer-by rate
Therapeutics			
explantation (battery, lead, ...)	procedure		passer-by rate
related medication	medication day		Pharmaceutical compass

Table EE1-S continued. Dutch unit costs (€) for resources used

Resource	Unit	Unit costs in 2020 euros	Source
Non-hospital care			
Medication			
CLI-cassettes related medication	cassettes medication days		Pharmaceutical compass Pharmaceutical compass
Out-of-hospital consultation			
general practitioner	visit		DMC
occupational therapist	visit		DMC
physiotherapist	visit		DMC
speech therapist	visit		DMC
dietician	visit		market price
social worker	visit		DMC
psychologist	visit		DMC
rehabilitation physician	visit		DMC
company physician	visit		DMC
Other institutional stay			
nursing home day	day		DMC
rehabilitation center day	day		DMC
Formal home care			
house holding	hour		DMC
personal	hour		DMC
home nursing	hour		DMC
Equipment			
walking devices	device		market price

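### The HEAP depreciates in-year replacements of the tube and pump system and the neurostimulator over five years, so each enters the 12-month costs at about one fifth of its unit cost

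*SAP*

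**What the plan says.** The rule is in the HEAP under Unit costs and costing. It covers "The unit costs of the (re)placement of the neurostimulator system and of the tube and pump system (re)placements". These are taken from hospital costing sheets and "subsequently capitalized based on a 5-year depreciation period". The stated reasons are that five years reflects the life of the equipment, and that the aim is a stable yearly cost difference that does not depend on the length of the study. The same section then says: "Costs of resources used were calculated by multiplying the frequency of distinct resources used with their respective (depreciated) unit costs". It describes no write-off of an item that fails early.

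The horizon, under Perspective, time horizon and discounting, is set "with a time horizon of 12 months following index surgery", without discounting.

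Protocol section 12.5 is narrower. It says "we will depreciate the initial add-on intervention costs (placement of neurostimulator for DBS and tube and pump placement for CLI) over five years", and gives as its reason "given the 5-year life-cycle of the studied devices (neurostimulator, tube, and pump". It says nothing about how replacements are to be charged.

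Under Additional sensitivity analyses, the HEAP varies the depreciation period from 5 years to 6, 7 and 8 years only.

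In Table EE1-S (Appendix IV) an asterisk marks the CLI pump, PEG-jejunostomy placement, "tube replacement" and (re)implantation. Electrode replacement, extension cable replacement, battery exchanges and explantation have none. The asterisk's footnote is cut off in the available text, and the unit-cost column is empty.

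**The concern.** Five-year depreciation is reasonable for a device that is expected to serve five years: one fifth of its cost belongs to the trial year. That reasoning fails for a device replaced within the year. The remaining four fifths of the original were lost inside the horizon, and the replacement is a further outlay. Under the HEAP rule the lost four fifths are charged nowhere.

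Cost is one half of both primary economic outcomes, and technical failure is part of what separates two device-based treatments. A rule that mutes replacement cost carries through to total costs, the ICER, the ICUR, net health benefit and the acceptability curves. No planned analysis would show how much it matters.

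**Working it through.** **Inputs.**
- Depreciation period L = 5 years (HEAP, Unit costs and costing). No interest rate is stated, so straight-line is assumed and the share charged in the year is 1/L.
- Patient cost = observed count × depreciated unit cost (same section).
- Horizon 12 months.
- Planning cost difference EUR 34,174 and willingness to pay EUR 120,000 per QALY (protocol section 4.4).
- Full unit cost C and replacement rate: not in the documents, so assumed below.

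The plan states no depreciated cost, so there is no figure to reproduce.

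**Step 1: charge per patient with r replacements in the year.**
- HEAP: (1 + r) × C/5.
- Initial placement depreciated, replacements in full: C/5 + r × C. Writing off each failed item and depreciating the surviving one gives the same total.

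| r | HEAP | Replacements in full | Gap |
|---|---|---|---|
| 0 | 0.2C | 0.2C | 0 |
| 1 | 0.4C | 1.2C | 0.8C |
| 2 | 0.6C | 2.2C | 1.6C |
| 3 | 0.8C | 3.2C | 2.4C |

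The gap is 0.8C per depreciated replacement. If an annuity with interest was meant (3% to 5% assumed), the share charged is 21.8% to 23.1% instead of 20%, which changes little.

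**Step 2: does the planned sensitivity analysis cover this?** The share charged is 1/6 = 16.7%, 1/7 = 14.3% and 1/8 = 12.5%. Every step moves away from full charging.

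**Step 3: size.** Mean undercharge per patient = 0.8 × replacements per patient × C. All rates and unit costs here are assumptions.

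| Rate | C (EUR) | Undercharge (EUR) | Share of 34,174 | QALY at 120,000 |
|---|---|---|---|---|
| 0.1 | 1,000 | 80 | 0.2% | 0.0007 |
| 0.3 | 5,000 | 1,200 | 3.5% | 0.010 |
| 0.5 | 5,000 | 2,000 | 5.9% | 0.017 |
| 1.0 | 5,000 | 4,000 | 11.7% | 0.033 |

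The result is linear in C. If a (re)implantation cost EUR 20,000 (also assumed), a rate of 0.1 would give 0.8 × 0.1 × 20,000 = EUR 1,600, or 4.7%. These are amounts within one arm. What enters the ICER is the difference between arms, and that cannot be computed from the documents.

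**Step 4: does the rule fit the HEAP's own aim of a yearly cost?** Let r be replacements per patient-year.
- If replacements recur at rate r on top of the five-year life, five years cost C + 5rC, which is C/5 + rC per year.
- If five years is a mean life that already includes early failures, the yearly cost is C/5, with nothing added for replacements.
- The HEAP charges C/5 + rC/5, which matches neither. It is correct only if the replacements seen in year one are all that occur in five years, and the documents do not claim that.

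**The case against.** The best defence is that the HEAP wants an annualised cost, not the cash spent in 12 months. If five years is an average life, C/5 already pays for early failures, and adding write-offs without crediting devices that outlast five years would overcharge. The documents do not say whether five years is a mean or a fixed life, so the point stands as a caution about the 0.8C figure. It does not rescue the rule, because step 4 shows that counting replacements at C/5 each does not follow from a mean life either.

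It is also fair that the protocol does not say replacements are charged in full. It names initial costs for depreciation and is silent on the rest. The HEAP therefore fills a gap, without giving a reason, and does not reverse a stated rule. It was also fixed before database lock.

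Three stronger readings are tempting, and the documents do not support them.
- A reader might infer that device failures are hidden. They are not: replacement counts appear by type and arm in Table EE2a and itemised costs in Table EE3a-S. Admissions, visits, imaging and explantation are separate items without a depreciation mark, and (serious) adverse events are listed.
- A reader might infer that every in-year component replacement is understated. The HEAP text covers the neurostimulator system and the tube and pump system. Electrode, cable and battery items carry no asterisk, and if the asterisk means depreciated they are charged in full.
- A reader might infer that the table treats the arms unequally and so favours CLI. That rests on an asterisk whose footnote is cut off. The text and table also do not map cleanly: the text cites costing sheets, while the table gives a passer-by rate for tube replacement, PEG placement and (re)implantation.

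**Conclusion.** The point holds for tube and pump system replacements and neurostimulator (re)implantations within the 12 months. Read as written, each is charged at about one fifth, and total costs, the ICER and the ICUR understate its cost by 0.8C. This assumes straight-line depreciation and that five years is the expected service life, not a mean that already includes failures.

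The amount may be negligible or moderate: about EUR 80 to 4,000 per patient over the assumed range. Nothing in the documents shows that it would change the conclusion against a planning difference of EUR 34,174. Its net direction is open, because both arms contain depreciated items and neither unit costs nor replacement rates are given. The case for acting is that the rule has no stated justification for replacements, goes beyond the protocol's wording, and is tested only in the direction that charges less.

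**What to change.** In the HEAP, under Unit costs and costing, limit depreciation to the initial placement, which is what protocol section 12.5 names. Charge tube and pump system replacements and neurostimulator (re)implantations within the 12 months at full unit cost, or write off the remaining value of the failed item, with one rule for both arms. Report the present fully depreciated version as a sensitivity analysis. If the base case is to stay, the minimum is to add full charging of in-year replacements beside the 6 to 8 year analysis.

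State whether five years is a mean or a fixed life. Complete the footnote to Table EE1-S, and check that tube replacement, (re)implantation, electrode, extension cable and battery items all follow the stated rule.

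The cost is a sentence or two of text and a small change in cost syntax. No new data are needed, because replacement counts are already planned by type and arm. The downside is a somewhat higher and more variable replacement cost.
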